- The primary efficacy endpoint will be compared for the active treatment to the placebo in the Full Analysis Set, including subjects in the A/A treatment sequence. In this analysis, the same method used in the analysis for the primary efficacy endpoint will be applied.
- The primary efficacy analysis will be repeated with exclusion of data after any major protocol deviation.

10.5.2 Multiple Imputation Analysis

Analysis based on imputing missing values by drop out reason (Protocol Section 4.4.1) are added as sensitivity analysis to the primary efficacy analysis. The primary imputation method within the sensitivity analysis will be the multiple imputation method for the Full Analysis Set described below in this section.

A subject is considered to have missing values in case he/she leaves the study prematurely. The fraction of non-missing data (f) and normalized number of HAE attacks (NNA_{observed}) will be determined per treatment period and subject as follows:

17 Aug	2017
--------	------

Category	Level of Participation per Treatment Period	Fraction of non-missing data (f) per Treatment Period	Observed normalized number of HAE attacks (NNA _{observed})
А	Subject is not discontinued from the study	1	As outlined in Section 8.1
В	Subject is discontinued from the study in a treatment period	Days of participation / scheduled length of treatment period (days)	As outlined in Section 8.1
С	Treatment period 2 among subjects who discontinued during treatment period 1	0	

Days of participation will be calculated as defined in Section 8.1 and scheduled length of treatment period is the intended length, i.e., 14 weeks for analysis equals $14 \times 7=98$ days.

The missing data will be imputed with NNA according to the sensitivity analysis by drop out reason. The normalized number of HAE attacks to be used for the sensitivity analysis (NNA_{analyzed}) will be calculated based on the observed number (NNA_{observed}) and the imputed number (NNA_{imputed}) taking into account the fraction of non-missing data (f) as:

 $NNA_{analyzed} = f \times NNA_{observed} + (1 - f) \times NNA_{imputed.}$ (Equation 10.1)

Values for NNA_{observed} will be determined as outlined in the above table; values for NNA_{imputed} will be determined for each subject and period with missing data depending on the sensitivity analysis as described below.

If a subject discontinues prematurely in treatment period 1, his/her NNA_{analyzed} value during treatment period 2 will be imputed by the median of the non-missing NNA_{observed} from all subjects who have complete data within the same treatment as that the subject is expected to take in treatment period 2.

If a subject discontinues prematurely from a treatment period, the remaining part of this period (NNA_{imputed}) will be imputed using the bootstrap method. The same imputation method used for treatment period 1 missing data will be used for treatment period 2 missing data

- 1. Draw a bootstrap sample with replacement from all Full Analysis Set subjects of the same treatment sequence with no missing values using PROC SURVEYSELECT with a seed of 300.
- 2. Use the following rules to calculate NNA_{imputed} for the missing data for each bootstrap sample.

Shire SHP616-300 Statistical Analysis Plan idursulfase IT

- a) Missing data are considered as missing at random (MAR) if the dropout reasons are not related to the investigational product and study termination by sponsor (subjectdid not want to be in this study, site was closing, other personal reasons). For subjects with MAR data, the value of NNA_{imputed} will be the median of NNA_{observed} of all subjects who have complete data within the same treatment.
- b) Data which are missing due to dropout for the following reasons are considered missing not at random (MNAR): discontinued due to AEs, death or lack of efficacy. For subjects with MNAR data, the median of the worst 25% observed data of the bootstrap sample from subjects who have complete data within the same treatment (x̃) will be determined. The value of NNA_{imputed} equals the maximum NNA_{observed} among all these subjects if NNA_{observed} > x̃, and x̃ otherwise.
- c) Data which are missing because of protocol violations, other, withdrawal by subjects, or physician decision will be reviewed, and a decision of classifying them into the categories as described in a) or b) will be made and documented prior to unblinding.
- 3. After NNA_{imputed} is calculated, use Equation 10.1 to calculate NNA_{analyzed}. The complete bootstrap sample with imputed values (NNA_{analyzed}) will be analyzed by fitting the primary analysis model
- 4. Repeat the above 3 steps for 1000 times.
- 5. The model adjusted summaries will be combined from the 1000 imputed bootstrap samples using Rubin's formulae from PROC MIANALYZE. These estimates include: the model adjusted NNA, the overall difference of NNA between the study drug and the placebo, and the type III tests p-values of fixed effects.

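### SAP 10.5.2 refits the primary model to resampled subjects and then pools with Rubin's formulae, so sampling variance is counted twice and, as worded, the sensitivity analysis reports too large a standard error

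*SAP*

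**What the plan says.** The opening of SAP 10.5.2 states that analyses imputing by dropout reason "are added as sensitivity analysis to the primary efficacy analysis", and that the main method "will be the multiple imputation method for the Full Analysis Set described below in this section". For a subject who stops partway through a period, the rest of that period "will be imputed using the bootstrap method". The numbered steps are then:

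- Step 1: "Draw a bootstrap sample with replacement from all Full Analysis Set subjects of the same treatment sequence with no missing values". No draw size is given, and no rule for how dropouts rejoin a sample drawn only from completers.
- Step 2: compute imputed attack rates "for the missing data for each bootstrap sample". Under 2a (missing at random, MAR) the value is the median "of all subjects who have complete data within the same treatment". Under 2b (missing not at random, MNAR) it comes from the worst quarter of the bootstrap sample, which is named explicitly. A wholly missed Period 2 is also filled with a treatment median.
- Step 3: the completed bootstrap sample "will be analyzed by fitting the primary analysis model".
- Steps 4 and 5: repeat 1000 times, then "The model adjusted summaries will be combined from the 1000 imputed bootstrap samples", using Rubin's formulae in PROC MIANALYZE.

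SAP section 16 lists no changes, and nothing else in the text available for review alters the pooling rule.

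**The concern.** Rubin's total variance is T = W + (1 + 1/M)B, where W is the average within-fit variance and B the variance between fits. It is valid when the M data sets share the same observed values and differ only in what was imputed, so that B carries imputation uncertainty alone. In steps 1 to 3 the observed subjects themselves are redrawn each time. B then contains the full sampling variance, which W already holds.

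This is the plan's main imputation-based check on dropout. The primary analysis only divides attacks by days on treatment, which SAP 10.1 describes as equivalent to last observation carried forward. An inflated standard error here can make a robust result look fragile. Because several steps are unstated, two programmers could also report standard errors that err in opposite directions.

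**Working it through.** **Inputs.** 26 + 26 crossover subjects (SAP Table 1). From SAP 2.5: 44 of them completing (hence 8/52 dropouts, 4 per sequence), difference 1.0 attacks per month, SD of the difference 2.0, one-sided alpha 0.025.

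**Plan's own figure.** With n = 44 the noncentrality is 1.0/(2.0/√44) = 3.317. The paired t-test with 43 df has power 0.900, and the normal approximation gives Φ(3.317 − 1.960) = 0.913. The stated 90% is reproduced, so the inputs are read correctly.

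**No dropout, closed form.** The treatment estimate is the average of the two sequence means of within-subject differences. Its variance is (4/26 + 4/26)/4 = 0.0769. Drawing n from n shrinks the expected sample variance by (n − 1)/n, so W = 0.0769 × 25/26 = 0.0740. B equals the same 0.0740. Then T = 0.0740 + 1.001 × 0.0740 = 0.1480, and the SE ratio is √(0.1480/0.0769) = 1.39. With 22 per sequence it is √(2 × 21/22) = 1.38. The SD cancels from the ratio. Nothing has been imputed, so a valid method would return 1.00. Simulation with 100 draws agrees: W = 0.0739, B = 0.0742, T = 0.0739 + 1.01 × 0.0742 = 0.1488, true variance 0.0782, ratio 1.38.

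**Planned dropout, simulation.** 6000 trials × 100 draws, with Monte Carlo error of each ratio about 1%. Assumptions not in the SAP: draw size equal to the completers in the sequence; half of dropouts in each period; uniform dropout time; within-subject correlation 0.5. Normal data, all MAR, 8/52:

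| Reading | W | B | T | True variance | SE ratio |
|---|---|---|---|---|---|
| Dropouts added back, medians fixed | 0.0693 | 0.0618 | 0.1317 | 0.0868 | 1.23 |
| Dropouts added back, medians per draw | 0.0693 | 0.0744 | 0.1444 | 0.0865 | 1.29 |
| Completers only | 0.0863 | 0.0864 | 0.1736 | 0.0941 | 1.36 |

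Adding runs with half the dropouts MNAR and with skewed counts (gamma frailty, placebo 3 and active 2 attacks per month) widens these to 1.23-1.30, 1.29-1.34 and 1.35-1.40. A separately coded simulation gave 1.27-1.33 with dropouts appended and 1.34-1.40 for completers only. It gave 1.20-1.28 if 26 per sequence are drawn from the completers, so draw size matters.

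**Effect on significance at 8/52.** Power is roughly Φ(1.0/SD − 1.96k), with k the SE ratio.

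- Fixed medians: 1/√0.0868 = 3.39; Φ(3.39 − 1.96 × 1.23) = Φ(0.98) = 84%, against Φ(1.43) = 92% with a calibrated SE.
- Per-draw medians: Φ(3.40 − 1.96 × 1.29) = Φ(0.87) = 81%.
- Completers only: Φ(3.26 − 1.96 × 1.36) = Φ(0.59) = 72% (simulated 73%), against a simulated 91%.

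**Heavier dropout (14/52, an assumption).** 1.14-1.21 with fixed medians, 1.25-1.27 with per-draw medians.

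**Donor-pool reading.** If the model is refitted to the original subjects and the bootstrap only supplies values, B/W is 0.01-0.03 at 8/52 and the SE ratio is 0.91-0.98, that is 2-9% too small. At 14/52 it is 6-14% too small. The cause is that every MAR subject receives a median with no random draw.

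**The case against.** The best counter-argument is that the bootstrap was meant only as the imputation device. The section calls itself a method for the Full Analysis Set, the sentence before step 1 speaks of imputing by bootstrap, and step 1 draws only complete subjects, who are natural donors. That is a fair reading of the intent, and under it the double counting disappears. It does not fit steps 3 and 5, where the bootstrap sample itself is fitted and pooled, and it leaves an SE that errs the other way.

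A reader might infer that the SE is 14-40% too large purely because steps are unstated. The documents do not support that range. The 14% end needs 14/52 dropout, a figure found nowhere in them. The 40% end comes from a completers-only sample, in which nothing is imputed, so it sits badly with step 3's reference to imputed values. Step 2b names the bootstrap sample as its source, while step 2a refers only to all subjects with complete data. That contrast favours fixed medians, although step 2's lead-in leaves some doubt.

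A reader might also infer a threat to the trial's conclusion. There is none: SAP 10.3 rests success solely on the primary analysis, this analysis sits under the exploratory heading 10.5 with no significance criterion of its own, and the literal error is conservative. Other sensitivity analyses are also listed in SAP 10.5.1.

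**Conclusion.** Wrong as written, and not merely under-specified: the stated combination of resampling, refitting and Rubin pooling inflates the SE by about 38% even when no data are missing. At the planned dropout the excess is about 23-34% with dropouts added back, more likely 23-30% on step 2a's wording, and 35-40% if only completers are refitted. These figures rest on the assumed draw size, dropout timing and data distributions; the no-dropout result assumes only that as many subjects are drawn as are observed. The direction reverses, modestly, under the donor-pool reading. With the effect exactly as planned, the literal analysis would miss significance in about 16-27% of trials instead of about 7-9%, and the shortfall would come from the variance rule rather than from dropout. It should be corrected, but neither the primary test nor its type 1 error is affected.

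**What to change.** Reword steps 1, 2, 3 and 5 before unblinding. Resample all crossover Full Analysis Set subjects within sequence, dropouts included, with draw size equal to the number in the sequence. Re-impute within each draw, with medians recomputed there, and refit the primary model. Take the SE and 95% CI from the 1000 bootstrap estimates and drop PROC MIANALYZE. The cost is a few sentences and a small programming change, with no effect on patients or the protocol. One small downside: this SE may be slightly small (ratio to the true SD about 0.93-1.02).

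Alternative: keep the original Full Analysis Set fixed, draw the imputed values with proper random variability instead of medians (including step 2a and the missed Period 2 values), and then apply Rubin's formulae. With random donor values from each bootstrap draw the ratio was 1.00-1.03 under MAR. The MNAR version was not tested and must be verified before use. This option also changes the Period 2 median rule that precedes the steps.

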11. SAFETY ANALYSES

The safety analyses will be performed by treatment using the Safety Set. Safety endpoints include adverse events (AE), clinical laboratory assessments, vital signs, ECG findings, SC injection site reactions, C1 INH antibody status and patient-reported tolerability of icatibant therapy for acute angioedema attacks. The last assessment prior to the first dose of investigational product in treatment period 1 will be used as baseline for all safety analyses.

11.1 Adverse Events

Adverse events will be coded using the Medical Dictionary for Regulatory Activities (MedDRA), Version 19.0 adverse events dictionary.

Adverse events will be collected from the time of informed consent through 7 days after the last dose date of investigational product. All serious adverse events (SAE) that occur \leq 30 days after the last dose date of investigational product and related SAEs that occur >30 days after the last dose date of investigational product will be collected.

An adverse event that increases in severity will be captured as a new event. An AE that develops into a SAE will be captured as a new event from the date it met the seriousness criteria. Worsening of pre-treatment events, after initiation of investigational product, will be recorded as new AE. An AE (classified by preferred term) that occurs during the study will be considered a treatment emergent adverse event (TEAE) if the start date and time of the AE is on or after the first dose date of investigational product and up to 7 days after the last dose of investigational product and up to 30 days after the last dose of investigational product, or with an increase in severity on or after the date and time of the first dose.

In addition, angioedema attacks and ISRs will not be considered AEs unless they satisfy serious criteria according to the protocol.

The number and percentage of subjects reporting any TEAEs, SAEs, and TEAEs related to investigational product, TEAEs leading to withdrawal, Severe TEAEs and absolute count of events will be summarized. Angioedema attacks and ISRs will not be considered AEs unless they satisfy serious criteria according to the protocol.

The number and percentage of subjects reporting any TEAEs, and absolute count of events will also be summarized in the following ways:

- By SOC, preferred term and treatment
- By SOC, preferred term, treatment and maximum severity
- By SOC, preferred term, treatment and relationship to investigational product in the opinion of the investigator
- By preferred term

TEAEs leading to withdrawal, SAEs, and deaths will be similarly summarized as TEAEs.

CONFIDENTIAL

Shire SHP616-300 Statistical Analysis Plan idursulfase IT

TEAEs related to investigational product, serious TEAEs related to investigational product and TEAEs related to investigational product leading to withdrawal will be similarly summarized as TEAEs. Summaries of TEAE or TEAE related to investigational product within 24 hours after the end of injection of investigational product will be provided by treatment.

A sensitivity analysis will be conducted by attributing TEAEs that occur during the first 2 weeks of Treatment Period 2 to Treatment Period 1 for the A/B (C1 INH to placebo treatment sequence.

To assess carryover effect with an assumption that it exists for both A/B and B/A treatment sequences, a sensitivity analysis will be conducted by excluding any TEAEs occurring within the first 2 weeks of Treatment Period 2, when carryover is suspected to be maximal.

All information about AEs collected on the eCRF will be listed alongside the treatment, preferred term, and SOC. Listings will also be provided on TEAEs related to investigational product, TEAEs leading to withdrawal, SAEs, and deaths.

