Subjects will remain outpatients throughout the study. Investigational product will be administered at the investigational site for Dosing Visits 1, 8, 16, 24, and 28 during both treatment periods. Other doses may be administered by qualified blinded personnel at the investigational site or at the subject's home or other agreed upon location or self-administered by the subject (adolescent or adult) with or without supervision (qualified home health professional or study site personnel), after receiving appropriate training by the investigator or designee. Adolescent subjects self-administering the investigational product will be supervised by a parent/legal guardian/caregiver (if home health professional and/or study site personnel is not present). Alternatively, a parent/legal guardian/caregiver after receiving appropriate training, will be allowed to administer the investigational product to an adolescent subject with or without supervision.

Throughout the study, an electronic subject diary will be used to record specific information regarding the subject's symptoms of HAE and details on self-administration as described in Sections [7.2.2.2](#) and [6.5.1](#) respectively. Additionally, quality of life questionnaires and surveys on SC administration of the investigational product will be also subject evaluated. Note: For adolescent subjects, a parent/legal guardian/caregiver is allowed to assist the subject in completing the electronic subject diary, including the quality of life questionnaires.

Adverse events will be recorded from the time the informed consent is signed through 7 days after the last dose of investigational product. This includes events occurring during the screening phase of the study, regardless of whether or not the investigational product is administered. In addition, the investigator will report all SAEs that occur through 30 days after the last dose of investigational product to Shire Pharmacovigilance and the respective Independent Reviewing Authority according to local reporting requirements.

A post-treatment visit will be performed at the investigative site 1 week (± 1 day) after the last dose of the investigational product in Treatment Period 2 for follow-up safety assessments. In addition, subjects will have blood samples collected for PK/PD and C1 INH antibody testing at 1 month (± 2) days after the last dose of the investigational product.

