8.2.4 Serious Adverse Event Collection Time Frame

All SAEs (regardless of relationship to study) are collected from the time the subject signs the informed consent until the defined follow-up period stated in Section 7.1.5, and must be reported to the Shire Pharmacovigilance Department and Medical Monitor within 24 hours of the first awareness of the event until 30 days after the last dose of investigational product.

In addition, any SAE(s) considered “related” to the investigational product and discovered by the investigator at any interval after the study has completed must be reported to the Shire Pharmacovigilance Department within 24 hours of the first awareness of the event.

Note: Investigators will report all SAEs that occur \leq 30 days after the last dose of investigational product and related SAEs that occur $>$ 30 days after the last dose of investigational product to Shire Pharmacovigilance Department.

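### SAP 11.1 gives treatment-emergent adverse events both a 7-day and a 30-day post-dose limit without saying which events each limit covers

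*SAP*

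**What the plan says.** SAP 11.1 first sets out collection, by event type. For AEs: "Adverse events will be collected from the time of informed consent through 7 days after the last dose date of investigational product". For SAEs, everything up to "30 days after the last dose date of investigational product and related SAEs that occur >30 days after the last dose date". The protocol agrees. Section 3.1 says "the investigator will report all SAEs that occur through 30 days after the last dose of investigational product", and Section 8.2.4 requires SAEs to be reported "within 24 hours of the first awareness of the event until 30 days after the last dose of investigational product".

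The next paragraph of SAP 11.1 defines a TEAE. It opens the window at first dosing and closes it with two limits given together: "up to 7 days after the last dose of investigational product and up to 30 days after the last dose of investigational product". The only other route is "or with an increase in severity on or after the date and time of the first dose". The sentence does not distinguish serious from non-serious events.

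Most safety tables use this definition: any TEAE, by SOC and preferred term, by maximum severity, and by relationship. Related events get the same set of tables, including a table of serious related TEAEs. SAEs and deaths also have their own summaries and listings, with no stated restriction to treatment-emergent events.

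**The concern.** The collection rule separates the two windows by event type and the TEAE rule does not. With both limits applied to every AE, the longer one is redundant, which suggests that the sentence does not say what was meant. A programmer following the text as written would apply 7 days to everything. One who inferred the intent would apply 30 days to SAEs. A third might take 30 days for all events. Each could claim to have followed the SAP.

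What is at stake is how serious events in late follow-up are classified. Confirmed thrombotic or thromboembolic events are, with limited exceptions, reported as SAEs under Protocol 7.2.3.9, so a late event of that kind is among those exposed. Under the literal coding it would be in the SAE table but not in the treatment-emergent tables.

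**Working it through.** No sample size, power or alpha figure bears on this, and the plan states no figure to reproduce. The check compares the possible windows. Let d be the onset day counted from the last dose.

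**Inputs.** The TEAE limits are 7 and 30 days, joined by *and* (SAP 11.1). AEs are collected to d = 7, all SAEs to d = 30, and related SAEs beyond that (SAP 11.1; Protocol 3.1 and 8.2.4).

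**Three readings of the onset limit.**

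| Reading | Rule | Last qualifying day, non-serious AE | Last qualifying day, SAE |
|---|---|---|---|
| Literal | d ≤ 7 and d ≤ 30, so d ≤ min(7, 30) | 7 | 7 |
| By event type | d ≤ 7 if non-serious; d ≤ 30 if serious | 7 | 30 |
| Longer limit for all | d ≤ max(7, 30) | 30 (but collected only to 7) | 30 |

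**Difference for SAEs.** Literal against by-type, the days affected are 8 to 30: 30 − 8 + 1 = 23 days.

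**Size in context.** As a share of post-treatment SAE follow-up, 23/30 = 77%. For a subject who completes both 14-week periods, the span from first dose to 30 days after the last is about 28 × 7 + 30 = 226 days, and 23/226 is about 10%. The second figure is the fairer one, because the wording has no effect while dosing continues.

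**Worked case.** SAP 11.1 gives an AE that turns serious a fresh record, dated from when it became serious. Suppose an AE starts on day 5 and becomes serious on day 10 with no change in severity grade. Under the literal reading the day-5 record is a TEAE and the day-10 serious record is not. Under the by-type reading both are.

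**Does another passage settle it?** Protocol 9.9 uses the term TEAE but gives no post-dose window. SAP 16 records no changes from the protocol. The SAP 11.1 sentence is therefore the only operative definition.

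**Related SAEs after day 30.** Their onset falls outside the limit under all three readings. The joining word does not cause that. The SAP simply does not say how they are classified.

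**The case against.** The best reply is that this is a dropped qualifier and that any competent reader will restore it. The same section has just given the same two numbers by event type, and the literal reading makes one of them pointless. That is a good argument about intent, and it stands. It does not supply the missing words, and a definition used for programming should not depend on inference.

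A reader might infer that serious events would disappear from the report. The documents do not support that. SAEs and deaths have their own summaries and listings, and all AE information on the eCRF is listed. Protocol 9.9 also calls for AEs of special interest to be summarized or listed, although SAP 11.1 names no such output. The route through increased severity has no upper time limit, so some events after day 7 would still qualify.

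It is also fair to say that SAE and TEAE counts can differ under any window. SAEs are collected from consent, so the SAE table, if unrestricted, can contain pre-dose events. The wording adds to that difference and is not its only source.

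Finally, 77% might be taken as the share of safety follow-up that is lost. It describes only the 30 days after the last dose, and it counts days, not events.

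**Conclusion.** The TEAE definition is wrong as written. It states two limits, assigns neither, and read literally leaves the second without effect. The consequence is limited to new-onset SAEs on days 8 to 30 after the final dose that do not qualify through increased severity. These would be collected and would appear in the SAE and death outputs, but would not count in the treatment-emergent tables, including the one for serious related TEAEs.

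This rests on two assumptions: that the sentence is coded as it stands, and that the SAE summary is not itself restricted to TEAEs, since the SAP states no such restriction. The documents give no event rate for late follow-up, so the number of events cannot be estimated. It is likely to be small. No efficacy result is touched.

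Two stronger inferences should be avoided. The text does not show a deliberate choice to exclude late SAEs, because the collection paragraph points the other way. Nor does this wording cause the exclusion of related SAEs after day 30. How to treat those is an open choice for the sponsor, and it needs to be stated.

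**What to change.** Rewrite the TEAE sentence in SAP 11.1 so that its limits follow the collection rule in the same section. In substance: an AE is treatment-emergent if it begins on or after the first dose and no later than 7 days after the last dose when non-serious, or no later than 30 days after the last dose when serious; or if its severity increases on or after the first dose.

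Add one line saying whether related SAEs with onset after day 30 are counted as TEAEs or only listed. Either can be defended, provided it is fixed before unblinding.

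The cost is two sentences in the SAP and a check that the programming specification matches. Data collection does not change and no protocol amendment is needed.
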